# 5. STUDY DESIGN

## 5.1. Study Description and Duration

This is a phase 4, OLE, uncontrolled, multi-center, long-term, safety study to be performed in patients who have completed the neurocognitive function study (R727-CL-1532). The observation period for PRALUENT treatment in the OLE study is planned to be approximately 192 weeks.

Patients who completed treatment and the EOS visit in the neurocognitive function study (R727-CL-1532) may enroll in the OLE study. The EOS visit of the double-blind neurocognitive function study (R727-CL-1532) corresponds to visit 1 (day 1) of the OLE study. The first SC injection of PRALUENT will be administered in the clinic (day 1, visit 1).

After visit 1, patients have the option to either self-administer study drug, or have another designated person (such as a spouse or caregiver) administer study drug for them.

The starting dose of PRALUENT will be 75 mg administered SC Q2W (regardless of treatment assigned in the neurocognitive function study R727-CL-1532), that may be modified to 150 mg administered SC Q2W, and can be maintained or modified from 150 mg Q2W to 75 mg Q2W. Low-density lipoprotein cholesterol levels must be measured at 8 weeks after initiating study treatment, or at least 4 weeks after dose modification, to assess response and to adjust the dose, if needed.

The investigator will be blinded to the treatment received in the neurocognitive function study (R727-CL-1532) until that study is complete and the database is locked. Lipid profile values from samples obtained after inclusion will be blinded until week 8, in order to prevent any potential unblinding of the neurocognitive function study (R727-CL-1532).

From week 8 in the OLE study, lipid measurements will be collected and will be known by the investigator in real time. The investigator will manage the PRALUENT dose at his/her discretion based on LDL-C levels, starting at week 12, by either modifying the dose from 75 mg Q2W to 150 mg Q2W, maintaining the dose, modifying the dose from 150 mg Q2W to 75 mg Q2W, or discontinuing treatment with PRALUENT at any time during the treatment period. If a dose is missed, the patient should administer the injection as soon as possible and thereafter resume treatment from the day of the missed dose (ie, resume on the next originally planned date). The statin dose should not be modified to adjust the degree of LDL-C lowering.

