Background LMT will be prescribed as per clinical practice and should remain the same as in the neurocognitive function study (R727-CL-1532). Lipid modifying therapy, including statins, should not be changed during the course of the study. However, if clinically necessary, background LMT may be adjusted at the investigator's discretion. Any adjustment will be

documented in the electronic case report form (CRF). Patients not treated with a statin (eg, statin intolerant patients, or patients in whom statin treatment was stopped during the neurocognitive function study [R727-CL-1532] for a safety reason) may still participate in the OLE study.

The investigator should refer to the label for information on PRALUENT and other LMTs.

Patients should continue a National Cholesterol Education Program-Adult Treatment Panel III Therapeutic Lifestyle Changes (NCEP-ATPIII TLC) diet or equivalent throughout the entire study duration.

Visits are planned at weeks 0, 8, 12, 24, 48, 72, 96, 120, 144, 168, and 192 (Figure 1). At each visit, except at the EOS visit at week 192, study drug will be dispensed to the patient. If at any time during the study after the week 8 visit, the investigator, based on lipid results or safety issues, decides to modify the dose of PRALUENT, an unscheduled kit dispensation visit will be performed.

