4.8. Other Variables

The other endpoints of the study will include:

- The percent change in hs-CRP from baseline to protocol specified visits. Hs-CRP values greater or equal to 10 mg/L will be excluded from analyses in a second approach, since these are suggestive of concurrent infection(1). PCSA (potentially clinically significant abnormalities) criteria for hs-CRP are listed in Appendix 10.2.
- The absolute change in HbA1c (%) from baseline to protocol specified visits. PCSA criteria for HbA1c are listed in Appendix 10.2.
- The proportion of patients with two consecutives results, separated by at least 21 days, of calculated LDL-C <25 mg/dL (<0.65 mmol/L) (and again for calculated LDL-C <15 mg/dL [< 0.39 mmol/L]) during the treatment period.
- For the patients with two consecutive results as described above, the time to the first calculated LDL-C <25 mg/dL (<0.65 mmol/L) (and again for calculated LDL-C <15 mg/dL [< 0.39 mmol/L]) during the treatment period.

Protocol schedule visits will be assigned to the Analysis Windows (See Appendix 10.1).

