- All grouping of TEAEs including adverse events of special interest, as listed in Section 4.7.1.2, will be presented by SMQ/CMQ and PT (when selection is based on SMQs/CMQs) and by SOC and PT (when selection is based on the e-CRF tick box or HLGT/HLT). The summaries will be sorted by decreasing incidence of PT within each SOC/SMQ (in the PRALUENT group).
- Neurocognitive events adjudicated by the neurocognitive events review committee will also be summarized by primary SOC and PT. They will also be summarized according to the adjudication of possible etiology of the neurocognitive events (Yes/No) (Section 4.7.1.2).
- All TEAEs within diabetes grouping will be analyzed overall and according to the diabetic status at baseline.
The following variables will also be tabulated for the local injection site reactions TEAEs:

- Intensity of the event (mild, moderate, severe);
- Number of events divided by the number of study treatment injections received;
- Time from first study treatment injection to first injection site reaction;
- Description of the highest intensity of each symptom recorded in the specific e-CRF page with table and bar chart.

Description of symptoms and possible etiologies for General Allergic Reaction TEAE reported by investigator (using the tick box), will be presented.

Post-treatment adverse events

- All post-treatment AEs by primary SOC and PT, sorted by the internationally agreed SOC order and decreasing incidence of PTs (in the PRALUENT group) within each SOC;
- All post-treatment SAEs by primary SOC and PT, sorted by the sorting order defined above.

Subgroup of patients with two consecutive LDL-C <25 mg/dL (<0.65 mmol/L)

If applicable, similar summaries of TEAEs as those described above will be provided on the safety subgroup population of patients with two consecutive results of LDL-C <25 mg/dL (as defined in Section 4.8) in both patient groups. Only TEAEs for which it will be confirmed or unclear that they occurred, worsened or became serious on the day or after the day the first level of LDL-C <25 mg/dL was observed will be considered in this summary.

In addition, the neurocognitive event rate in patients with 2 consecutive results separated by at least 21 days for calculated LDL-C <25 mg/dL, and calculated LDL-C <15 mg/dL, will be assessed.

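### The very-low-LDL-C safety subgroup is defined by a second low value but counts events from the first, so deaths between the two are excluded by construction and the subgroup death rate is understated

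*SAP*

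**What the plan says.** SAP 5.7.1 provides, if applicable, for repeating the TEAE summaries in the "safety subgroup population of patients with two consecutive results of LDL-C <25 mg/dL", pointing to SAP 4.8 for the definition. SAP 4.8 describes "two consecutives results, separated by at least 21 days, of calculated LDL-C <25 mg/dL". TEAEs are dated by onset, worsening or change to serious status, and only those "on the day or after the day the first level of LDL-C <25 mg/dL was observed will be considered in this summary". SAP 5.7.1 also plans a neurocognitive event rate for patients with confirmed values below 25 and below 15 mg/dL. It states no start for either events or time in that rate.

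Protocol 5.1 sets the visits: "Visits are planned at weeks 0, 8, 12, 24, 48, 72, 96, 120, 144, 168, and 192". In Protocol Table 1 the post-dose lipid panel is marked at every one of these except week 12, and also in the combined end-of-treatment and early termination column. Investigators see the results: "From week 8 in the OLE study, lipid measurements will be collected and will be known by the investigator in real time".

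The only person-time rule in SAP 5.7.1 gives an event-free patient the whole TEAE period, which under SAP 4.7.1 begins at the first dose in this extension study.

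**The concern.** Requiring two values is a sensible way to define sustained very low LDL-C. The difficulty is the start of counting. Every member is known to have been alive at the second value, so the interval from first to second value contributes time but cannot contribute a death. This is immortal time. Correcting the denominator alone, while keeping the first value as the start, leaves it in place.

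This subgroup is the only place in SAP 5.7.1 where adverse events are broken down by achieved LDL-C. SAP 1.1 records that the clinical impact of prolonged very low LDL-C had been listed as missing information in the EU risk management plan until its removal. A reader with that question would look at this table, and for deaths its error always runs towards apparent safety. The death summaries in SAP 5.7.1.1 are complete but not split by LDL-C, so they do not correct it.

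**Working it through.** The documents give no rate or event count for this subgroup, so there is no planned figure to reproduce.

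**Gap (g).** The minimum is 21 days, or 3 weeks (SAP 4.8). From the Table 1 lipid schedule it is 24 − 8 = 16 weeks after a first low value at week 8, and 24 weeks after a later one.

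**Follow-up from the first low value (F), assumed.** First low value at week 8 or 24, with follow-up ending at week 96 or 192:
- 96 − 24 = 72 weeks
- 96 − 8 = 88 weeks
- 192 − 24 = 168 weeks
- 192 − 8 = 184 weeks

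**Deaths, constant hazard λ.** Members survive g and are then at risk for F − g, so

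observed rate = [1 − exp(−λ(F − g))] / [g + (1 − exp(−λ(F − g)))/λ].

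When λF is small, observed/true is close to (F − g)/F, so the assumed death rate hardly matters. With λ assumed at 1.5 per 100 patient-years (0.015/52 per week):

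| g (weeks) | F (weeks) | (F − g)/F | Exact ratio |
|---|---|---|---|
| 3 | 72 | 0.958 | 0.958 |
| 3 | 184 | 0.984 | 0.983 |
| 16 | 88 | 0.818 | 0.817 |
| 16 | 184 | 0.913 | 0.911 |
| 24 | 72 | 0.667 | 0.665 |
| 24 | 168 | 0.857 | 0.855 |

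For g = 24 and F = 72, the numerator is 1 − exp(−0.01385) = 0.01375. The denominator is 24 + 47.7 = 71.7 weeks, or 1.378 years. The observed rate is 0.0100 per year against 0.0150. Shorter follow-up is worse: a first low value at week 48 with follow-up ending at week 96 gives (48 − 24)/48 = 0.50.

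**After the change.** Starting events and time at the second value removes g from the denominator, and the expression reduces to λ, a ratio of 1.00. Following everyone from the first low value gives [1 − exp(−λF)] / {[1 − exp(−λF)]/λ} = λ, again 1.00.

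**Non-fatal events.** These were simulated in 400,000 patients from the first low value. All of the following are assumptions:
- Per 100 patient-years: death 1.5, stopping 5, non-fatal event 4.
- A 70% chance that the next value is again below 25 mg/dL, or 30% after a dose reduction, which 10% receive.
- An early termination sample 2 weeks after stopping.

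Ratio of cumulative incidence, subgroup to all patients with a first low value:
- No event causes stopping: 1.01 to 1.02.
- Half cause stopping and no early termination value qualifies: 0.97 (g = 16, F = 184), 0.92 (g = 16, F = 88), 0.86 (g = 24, F = 72).
- Half cause stopping and 70% of early termination values are below 25 mg/dL: 1.00 to 1.01.

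The death-rate ratios in the same runs were 0.65 to 0.91, in line with the closed form.

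**Person-time, a separate effect.** If time ran from first extension dose while events ran from the first low value, the lead-in alone would multiply the rate by 184/192 = 0.96 (first low at week 8, end at week 192) to 72/96 = 0.75 (first low at week 24, end at week 96).

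**The case against.** A reader might infer that patients who stop for an adverse event or are down-titrated are also excluded by construction, and that risk at very low LDL-C is therefore understated in general. The documents do not support this.

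- **Stopping.** The early termination visit includes the lipid panel. It falls within 5 days of the decision to stop (footnote 1 to Table 1) or within 1 month of the last injection (Protocol 8.1.2). A value below 25 mg/dL there, at least 21 days after the first, qualifies the patient, taking that sample as part of the treatment period.
- **Dose reduction.** The only reduction described is from 150 to 75 mg (Protocol 5.1 and 7.3.1), and everyone starts on 75 mg. A reduced patient is lost only if the next value does not qualify. If that value is 25 mg/dL or above, exclusion follows from the definition of sustained low LDL-C.
- **Non-fatal events.** Members' events between the two values are counted, and the bias is about nil unless events lead to stopping.

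Three further points stand. Unscheduled values may be used (SAP 6.5), so some gaps will be shorter than 16 weeks. The wording on the first level most naturally means the first of the qualifying pair, as SAP 5.8 puts it for the time-to-event analysis, so it needs only a clarification. The table is conditional and descriptive, SAP 1.1 does not assign it to the risk-management question, and all deaths, serious TEAEs and discontinuations are still reported for the full safety set.

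A landmark at the second value also has a price: it drops members' events during a period of documented low LDL-C. That is a reason for a companion table, not for keeping the present rule. None of these points removes the exclusion of deaths.

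**Conclusion.** The point holds for deaths. As written, the rule excludes every death between the two values and understates the subgroup death rate by about g/F: 2 to 33% over gaps of 3 to 24 weeks and follow-up of 72 to 184 weeks, and more with shorter follow-up. This rests on a constant hazard and assumed follow-up. The documents give neither the timing of first low values nor the follow-up achieved before the sponsor ended the study early, so the size in this trial cannot be known.

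For patients who stop or have a dose reduction, loss is conditional: the next or early termination LDL-C must be 25 mg/dL or above, missing, or less than 21 days after the first. For non-fatal TEAEs that do not lead to stopping, no material bias was found. The fault is confined to one supplementary descriptive summary and the neurocognitive rates beside it.

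**What to change.** In SAP 5.7.1:

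1. For the confirmed-low subgroup, start both event counting and person-time at the second, qualifying value.
2. Add a companion summary of all patients with at least one LDL-C below 25 mg/dL, with events and person-time from that first value, so that deaths and stops between the values are shown.
3. Apply both to the 15 mg/dL threshold and to the neurocognitive event rates, stating the start of events and time for each.
4. State that the general person-time rule, which runs from first extension dose, does not apply to these tables.
5. Say explicitly which value the first level means.

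The cost is SAP wording, a changed start date in programming and one additional set of tables from data already collected. The confirmed-low table will have fewer events, and the companion table will include some patients whose low LDL-C was not sustained. The two should therefore be read together.

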5.7.1.1. Patient Deaths

The following summaries of deaths will be generated.

- Number (%) of patients who died by study period (TEAE and post-treatment);
- Deaths in enrolled but not treated patients;
- TEAEs leading to death (death as an outcome on the AE CRF page, as reported by the Investigator) by (at least) SOC (sorted by internationally agreed order), and PT (sorted by decreasing frequency, showing the number (n) and percentage (%) of patients) for the safety population.

5.7.2. Analysis of Clinical Laboratory Variables

Clinical laboratory parameter actual values (quantitative) and change from baseline values will be descriptively summarized at baseline and each post-baseline visit (collected up to the day of last dose of study treatment +21 days) by at least patient number, mean, median, Q1, Q3, SD, minimum and maximum for each patient group. Additionally, laboratory parameter measures for last on-treatment values and worst on-treatment values will be summarized in a similar manner. Clinical laboratory parameters mean changes from baseline, with the corresponding SE, can be plotted at each visit, in the case results warrant further investigation. These parameters will be presented by the biological functions defined in Section 4.7.2. For glucose, only fasting samples will be included in the summaries.

Individual patient laboratory parameter measurements will be additionally evaluated by PCSA criteria, specifically identifying patients with at least one post-baseline measurement that meets the PCSA criteria within the TEAE period. The following additional project specific PCSA criteria will also be evaluated during the TEAE period:

- Patients with a hemoglobin decrease from baseline ≥ 15 g/L.
- Patients meeting the ALT increase defined in Section 4.7.1.2.
- Glucose (quantitative summary and PCSA) will also be analyzed, overall and according to the diabetic status at baseline.

Patients meeting the PCSA criteria at least once will be summarized by patient count (and percent) for a post-baseline PCSA measurement while accounting for the baseline PCSA status (PSCA normal/missing; PCSA abnormal), for each patient group. For the appendix, this laboratory parameter PCSA table will be reproduced with patients meeting the PCSA criteria at least once during the TEAE period regardless of baseline PCSA status. These laboratory parameters will be presented by the biological functions defined in Section 4.7.2. Patient listings of laboratory measurements that meet PCSA criteria will be provided for the report appendix. For those laboratory parameters that don't have an associated PCSA criteria, similar summary tables can be provided based on measurements outside the central laboratory normal ranges, if applicable.

Drug-induced liver injury

The liver function tests, namely AST, ALT, ALP, and total bilirubin, are used to assess possible drug-induced liver toxicity. The proportion of patients with PCSA values or ALT increase as defined as AESI (see Section 4.7.1.2) during TEAE period by baseline status will be displayed for each parameter.

An evaluation of drug-induced serious hepatotoxicity (eDISH) with the graph of distribution of peak values of ALT versus peak values of total bilirubin will also be presented using postbaseline values during TEAE period. Note that the ALT and total bilirubin values are presented on a logarithmic scale. The graph will be divided into 4 quadrants with a vertical line corresponding to 3 x ULN for ALT and a horizontal line corresponding to 2 x ULN for total bilirubin.

Listing of possible Hy's law cases identified (i.e., patients with any elevated ALT>3 x ULN, and associated with an increase in bilirubin >2 x ULN, concomitantly or not) with ALT, AST, ALP, total bilirubin, and if available direct and indirect bilirubin will be provided.

The incidence of liver-related TEAEs will be summarized. The selection of PTs will be based on SMQ Hepatic disorder (see Section 4.7.1.2).

5.7.3. Analysis of Vital Sign Variables

The vital sign actual values and change from baseline values obtained while sitting will be descriptively summarized at baseline and each post-baseline visit (collected up to the day of last dose of study treatment +21 days) by at least patient number, mean, median, Q1, Q3, SD, minimum and maximum for each patient group. Additionally, vital sign measures for last on-treatment value and worst on-treatment value will be summarized in a similar manner. Vital sign mean changes from baseline, with the corresponding SE, can be plotted at each visit, in the case results warrant further investigation.

Individual patient vital sign measurements (regardless of sitting position) will be additionally evaluated by PCSA criteria, specifically identifying patients with at least one post-baseline measurement that meets the PCSA criteria within the TEAE period. Patients meeting the PCSA criteria at least once will be summarized by patient count (and percent) and patient group. Patient listings of vial sign measurements that meet PCSA criteria will be provided for the report appendix.

5.8. Analysis of Other Variables

The summary of other variables will be presented on the safety population. No formal inferential testing will be performed for either period. Summaries will be descriptive in nature.

All measurements, scheduled or unscheduled, fasting or not fasting, will be assigned to analysis windows in order to provide an assessment for week 8 to week 96 time points.

Hs-CRP and HbA1cparameters (Section 4.8) will be summarized for the number of patients with data, mean, SD, median, minimum, and maximum (for hs-CRP, Q1 and Q3 will be also provided) by analysis visit during the treatment period. For HbA1c, summaries will also be provided according to diabetes mellitus status at baseline. The time profile will be plotted for HbA1c showing the means and the corresponding SEs, while medians (with Q1-Q3) will be plotted for hs-CRP. Applying the PCSA criteria to these variables at any time during the TEAE period, the number of patients (and percentages) meeting the criteria will be summarized.

The gonadal hormone parameters (Section 4.6.2) will be summarized for the number of patients with data, mean, SD, median, minimum, and maximum by analysis visit during the treatment period. For FSH and LH, the summaries will be performed for all patients, female patients, and male patients. Estradiol will be summarized for female patients only, and testosterone will be summarized for male patients only. Summary tables will also be provided for gonadal hormone parameters based on measurements outside the central laboratory normal ranges, if applicable. When appropriate, for female patients the gonadal-gonadotrophin in menopausal and non-menopausal women will be summarized separately.

In order to minimize confounding factors with menopause or exogenous estrogens, the summaries of estradiol, FSH, and LH for female patients will be repeated by excluding patients who were receiving hormone replacement therapy, were \geq 50 years, or had FSH levels \geq 25 IU/L at baseline.

For male patients, the summaries of testosterone, FSH, and LH will be repeated by excluding patients who were receiving testosterone supplementation or had LH levels ≥ 15 IU/L at baseline.

Binary endpoints defined in Section 4.8 will be described through patient counts and percentages. Kaplan-Meier curves will be provided for the variables assessing time to first occurrence of an event (i.e., calculated LDL-C related outcome). Patients not meeting the event will be censored at the end of the treatment period. For the analysis of the time to the first of the two consecutive LDL-C events, patients without post-baseline LDL-C result or with only one post-baseline LDL-C result will not be included in the analysis.

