#### 8.1.1. Footnotes for the Schedule of Events Table

- 1. Patients who prematurely discontinue study treatment: any study treatment discontinuation should be initially considered temporary, and the investigator should make every effort to resume study drug treatment as early as possible, pending no safety concerns, and to perform all study visits and assessments as usual. When a treatment discontinuation is considered 'permanent', an extra visit (early termination visit) should be performed within 5 days of the decision to permanently discontinue study drug. This visit will be the last visit for the patient.
- 2. The end of study (EOS) visit of the double-blind neurocognitive function study (R727-CL-1532) corresponds to visit 1 (day 1) of the OLE study. Patients may enroll in the OLE study after completing treatment and the EOS visit in the neurocognitive function study (R727-CL-1532). The first SC injection of PRALUENT will be administered in the clinic (day 1, visit 1). After visit 1, patients have the option to either self-administer study drug, or have another designated person (such as a spouse or caregiver) administer study drug for them. Study drug should be administered Q2 weeks throughout the study.
- 3. The kit will include study drug and the study drug compliance log.
- 4. If at any time during the study after the week 8 visit, the investigator, based on lipid results or safety issue, decides to modify the dose of study drug, an unscheduled kit dispensation visit will be performed. During this visit, a call to the IVRS/IWRS will be performed.
- 5. Concomitant medication: received concomitantly to the study drug, from the time of informed consent to the final study visit.
- 6. Alcohol consumption within 48 hours and intense physical exercise within 24 hours prior to blood sampling for lipid parameters are discouraged.
- 7. Assessments completed at EOS in the neurocognitive function study (R727-CL-1532).
- 8. For male patients (luteinizing hormone [LH], follicle-stimulating hormone [FSH], and testosterone) and for female patients (LH, FSH, and estradiol). Menstrual cycle data will be collected for women of childbearing potential who are not on hormonal contraceptives.

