1.1. Background/Rationale

This study is an open-label extension (OLE) to the neurocognitive function study (R727-CL-1532) in which all patients will be treated, in a single arm, with PRALUENT. The study will be conducted on patients who completed treatment and the end of study (EOS) visit in the neurocognitive function study (R727-CL-1532), with no premature discontinuation of study drug or placebo. This will allow for patient exposure to PRALUENT of approximately 6 years.

At the time of inclusion into the OLE study, knowledge of the treatment arm in the neurocognitive function study (R727-CL-1532) will not be available to the investigator or the sponsor. Patients eligible to participate in the OLE study will initiate treatment with PRALUENT at the starting dose of 75 mg once every 2 weeks (Q2W), regardless of the treatment group to which they were randomized in the neurocognitive function study (R727-CL-1532).

The study duration of approximately 192 weeks, in addition to the 96-week exposure in the neurocognitive function study (R727-CL-1532), will enable the assessment of long-term exposure to PRALUENT.

Following a Type II variation for Praluent submitted on 14 August 2019 to modify the EU RMP, the missing information "clinical impact of very low LDL-C for extended period of time" was removed from the RMP in the CHMP opinion dated Jan. 16,2020. The EMA agreed to release the R727-CL-1609 study as there is no expectation that this study can further characterize the safety profile of alirocumab beyond what has already been learned from other long-term, controlled studies. Therefore, the study was terminated early by sponsor on January 31, 2020. Given this early termination, all analyses will be considered descriptive.

PRALUENT is also referred to as alirocumab, REGN727 or SAR236553. In the context of the R727-CL-1609 SAP, it will be referred to as PRALUENT.

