2.3. Study Plan

From week 8 in the OLE study, lipid measurements will be collected and will be known by the investigator in real time. The investigator will manage the PRALUENT dose at his/her discretion based on LDL-C levels, starting at week 12, by either modifying the dose from 75 mg Q2W to 150 mg Q2W, maintaining the dose, modifying the dose from 150 mg Q2W to 75 mg Q2W, or discontinuing treatment with PRALUENT at any time during the treatment period. If a dose is missed, the patient should administer the injection as soon as possible and thereafter resume treatment from the day of the missed dose (ie, resume on the next originally

planned date). The statin dose should not be modified to adjust the degree of LDL-C lowering.

Background LMT will be prescribed as per clinical practice and should remain the same as in the neurocognitive function study (R727-CL-1532). Lipid modifying therapy, including statins, should not be changed during the course of the study. However, if clinically necessary, background LMT may be adjusted at the investigator's discretion. Any adjustment will be documented in the electronic case report form (CRF). Patients not treated with a statin (eg, statin intolerant patients, or patients in whom statin treatment was stopped during the neurocognitive function study [R727 CL 1532] for a safety reason) may still participate in the OLE study.

The investigator should refer to the label for information on PRALUENT and other LMTs.

Patients should continue a National Cholesterol Education Program-Adult Treatment Panel III Therapeutic Lifestyle Changes (NCEP-ATPIII TLC) diet or equivalent throughout the entire study duration.

Visits are planned at weeks 0, 8, 12, 24, 48, 72, 96, 120, 144, 168, and 192. At each visit, except at the EOS visit at week 192, study drug will be dispensed to the patient. If at any time during the study after the week 8 visit, the investigator, based on lipid results or safety issues, decides to modify the dose of PRALUENT, an unscheduled kit dispensation visit will be performed.

Figure 1: Study Flow Diagram

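### SAP 5.8 keeps event-free patients at risk past their last confirmable LDL-C sample, so the Kaplan-Meier curve for confirmed LDL-C <25 or <15 mg/dL is biased low, by an amount the documents do not fix.

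*SAP*

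**What the plan says.** SAP 4.8 lists two linked variables. The first is binary: "The proportion of patients with two consecutives results, separated by at least 21 days, of calculated LDL-C <25 mg/dL", repeated for <15 mg/dL. The second is a time: "For the patients with two consecutive results as described above, the time to the first calculated LDL-C <25 mg/dL", again repeated for <15 mg/dL.

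SAP 5.8 plans Kaplan-Meier curves for the time variable, measured to the first result of the pair. Its censoring rule is "Patients not meeting the event will be censored at the end of the treatment period". Its one safeguard is that "patients without post-baseline LDL-C result or with only one post-baseline LDL-C result will not be included in the analysis".

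Three other places set the sampling pattern:

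- SAP 2.3: "Visits are planned at weeks 0, 8, 12, 24, 48, 72, 96, 120, 144, 168, and 192". Table 1 of the protocol shows no lipid sample at week 12, so planned post-baseline LDL-C samples fall at weeks 8, 24, 48, 72, 96, 120, 144, 168 and 192.
- Protocol 8.1.1, footnote 1, on the early termination visit: "This visit will be the last visit for the patient".
- SAP 1.1: "the study was terminated early by sponsor on January 31, 2020".

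**The concern.** An event can be dated only at a sample that has a later sample at least 21 days after it. The closing sample never does. A patient whose closing value is low, and whose earlier values were not, is recorded as event-free at a time when no event could have been recorded for that patient. The risk set is too large by the number of such patients, so the estimated hazard is too small.

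The exclusion of patients with no or one result shows that the SAP accepts the principle that someone who cannot meet the definition should not count as event-free. It does not apply that principle to the last sample of everyone else. The early stop makes this relevant, because patients who enrolled at different times will have closing samples spread along the schedule.

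What is at stake is how often confirmed very low LDL-C is reported to occur over time. In a long-term safety study, understatement is the less cautious direction.

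The wording also conflicts. Taken alone, SAP 4.8 restricts the time variable to patients who had the event, whereas SAP 5.8 censors patients who did not.

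**Working it through.** The plan states no figure for this analysis, so there is none to reproduce.

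**Inputs from the documents.** The event definition, censoring rule, exclusion rule and sampling weeks are as set out above. There are nine planned samples, j = 1 to 9.

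**Inputs assumed.** The documents give no LDL-C distribution, event rate or closing dates. I take a constant chance p = 3%, 5% or 10% per sample of starting a low run that persists. Closing time is unrelated to LDL-C, and the treatment period ends at the closing sample.

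**Formula.** Let f(j) be the share of patients at risk at sample j who have a later sample at least 21 days on. Then:

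- true cumulative incidence at sample k = 1 − (1 − p)^k
- SAP rule = 1 − Π [1 − p·f(j)], over j = 1 to k

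Since f(j) ≤ 1, the SAP rule cannot raise the expected curve. Censoring at the last confirmable sample restores f(j) = 1.

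**Small example.** Take five samples, with patients closing equally at sample 2, 3, 4 or 5, and an assumed hazard of 10% at the first sample and 3% afterwards.

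- Corrected: 1 − 0.90 × 0.97³ = 17.9%.
- SAP rule: f = 1, 3/4, 2/3, 1/2, so 1 − 0.90 × 0.9775 × 0.98 × 0.985 = 15.1%.

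**Case A: closing on a scheduled visit**, uniform over the eight lipid visits from week 24 to 192. Here f(1) = 1 and f(j) = (9 − j)/(10 − j) afterwards: 7/8, 6/7, 5/6, 4/5, 3/4, 2/3 for weeks 24 to 144. For p = 5% at week 96: 1 − 0.95 × 0.95625 × 0.95714 × 0.95833 × 0.96 = 20.0%, against 1 − 0.95⁵ = 22.6%.

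**Case B: closing on any day**, uniform over weeks 24 to 192. A patient closing at week 60 was properly at risk at week 48, because the closing sample can confirm it, and has left before week 72. Only those closing within 3 weeks after a visit are wrongly at risk there, so f = (189 − w)/(192 − w) at week w ≥ 24. For p = 5% at week 96: 1 − 0.95 × 0.95089 × 0.95104 × 0.95125 × 0.95156 = 22.2%.

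| p | Week | True | Case A | Relative loss | Case B | Relative loss |
|---|---|---|---|---|---|---|
| 3% | 96 | 14.1% | 12.4% | 12% | 13.9% | 1.8% |
| 5% | 96 | 22.6% | 20.0% | 12% | 22.2% | 1.7% |
| 10% | 96 | 41.0% | 36.7% | 10% | 40.3% | 1.5% |
| 3% | 144 | 19.2% | 16.1% | 16% | 18.7% | 2.6% |
| 5% | 144 | 30.2% | 25.6% | 15% | 29.4% | 2.4% |
| 10% | 144 | 52.2% | 45.3% | 13% | 51.1% | 2.0% |

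Simulations of the same model agree within sampling error. Their range is 10 to 17% for case A (the upper end is 16.0% against 19.2%) and 0 to about 2% for case B. Simulated with the corrected censoring date, both cases return the true values to within about 0.2 points.

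**Early clustering.** With an assumed 10% at week 8 and 1% per sample afterwards, case A at week 96 gives 1 − 0.90 × 0.99125 × 0.99143 × 0.99167 × 0.992 = 13.0%, against 1 − 0.90 × 0.99⁴ = 13.5%. The loss is about 4% relative.

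**A different model.** Individual LDL-C values were simulated around an assumed on-treatment median of 50 mg/dL, for the <25 mg/dL threshold.

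- On-schedule closing over weeks 8 to 192: 7.3% against true 8.1% at week 96, and 8.2% against 9.7% at week 144. Corrected censoring gives 8.2% and 9.6%.
- Closing between visits: 9.5% against 9.6% at week 144 (follow-up 8 to 192 weeks), and 6.7% against 7.0% at week 72 (follow-up 8 to 96 weeks).
- Follow-up of only 8 to 96 weeks with on-schedule closing is the worst case: 4.9% against 7.2% at week 72. Few patients remain there, and the correction recovers only 6.5%.
- Everyone followed to week 192: no difference up to week 168, then a flat tail (10.1% against 10.7%).

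**The case against.** The strongest objection concerns size. The larger losses arise because patients close exactly on the visits where other patients' events are counted. A stop by the sponsor on one calendar date, with an early termination visit within 5 days of the decision to stop drug (Protocol 8.1.1) or within a month of the last injection (Protocol 8.1.2), makes closing between visits plausible. The loss is then a few percent at most. This stands: a reader might take 10 to 17% as the expected bias, and the documents do not support that, because they give no closing dates.

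The end of the treatment period is also not defined for this analysis. If it meant the last injection, before the closing sample, most of the bias would go. If it meant the last visit, as for the TEAE period in SAP 4.7.1, or last dose plus 21 days, as for laboratory summaries in SAP 5.7.2, the bias remains. That ambiguity is itself a reason to state the date.

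Three further inferences are tempting but unsupported:

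- **That the adverse-event subgroup in SAP 5.7.1 is affected.** It uses the two-result definition, not the censoring rule. No patient enters or leaves it, and the number of patients with the event is likewise unchanged.
- **That confirmation always takes 24 weeks.** The gap from week 8 to week 24 is 16 weeks. LDL-C is also measured at least 4 weeks after a dose modification (SAP 2.1), and unscheduled values may be used (SAP 6.5).
- **That the curve must reach 100% because SAP 4.8 admits only patients with the event.** Read with SAP 5.8, the intent is clear enough to program. This is loose wording to reconcile, not a second failure.

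Finally, the variable is outside the primary and secondary endpoints and no test depends on it. That limits the importance but does not make the rule correct.

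**Conclusion.** The censoring rule is wrong as written, and its bias runs downward. Both follow from SAP 4.8 and 5.8 without any assumed event rate, provided that closing time is unrelated to LDL-C and that the treatment period runs to the closing sample or beyond.

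The size is an assumption. With onset of 3 to 10% per sample and follow-up staggered to week 192, it is about 0 to 5% relative if closing samples mostly fall between scheduled visits and about 10 to 17% if they fall on them. It is less if low values appear mainly at the first samples. It can be larger late in a short follow-up that closes on schedule. It is nil before the last interval if everyone reaches week 192.

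Severity is minor. The result is descriptive, and no primary or secondary endpoint changes.

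**What to change.** In SAP 5.8, censor event-free patients at the date of their last on-treatment LDL-C that is followed by another LDL-C at least 21 days later, and include only patients with at least one such pair. This extends the existing exclusion to two results taken less than 21 days apart, and removes the dependence on an undefined end of treatment.

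In SAP 4.8, reword the time variable so that it covers all evaluable patients: those with a confirmed low result are dated at the first result of the pair, and the others are censored as in 5.8.

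The cost is a short text change in two SAP sections and one derived date per patient. The curve ends about one sampling interval earlier, and that last stretch cannot be recovered, because no event could be dated there.
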